Cover page

Official Title of the study:

Investigation of Real-time Diagnostic Ultrasound as a Means of Biofeedback Training in Transversus Abdominus Re-education of Patients With Non-specific Low Back Pain: Prospective Randomized Controlled Pilot Study

Date of the document: 4/5/2023

Document Type: Study Protocol with SAP

Background: It is believed that ultrasound-guided imaging of activation/contraction of the deep abdominal muscles (such as transversus abdominis) is useful for assisting deep muscle re-education, which is often dysfunctional in non-specific low back pain (NSLBP).

Objective: This pilot study's objective was to evaluate the use of real-time ultrasound (US) as a feedback device for transverse abdominis (TrA) activation/contraction during an exercise program in chronic NSLBP patients.

Methods: Chronic NSLBP patients are recruited and randomly assigned to an US-guided or control group. The same motor control-based exercise program is applied to both groups. All patients receive physiotherapy twice per week for 7 weeks. Outcome measures, test at baseline and post-intervention, include Numeric Pain Rating Scale (NPRS), TrA activation level (measured through a pressure biofeedback unit-based developed protocol), seven established motor control tests, Roland-Morris Disability Questionnaire (RMDQ) and Hospital Anxiety and Depression Scale (HADS).

Statistical Analysis Plan: Analysis of variance utilizing a two-way mixed analysis of variance (ANOVA) model for dependent measures of two factors (treatment group and time point of measurement) of which only one is repeated (time point of measurement) is performed to determine whether there were between- and within-group differences before and after treatment. Independent samples' t-test and paired samples' t-test are also used for differences between and within groups, respectively. An χ^2 test was also conducted for differences on the motor control tests and the TrA activation level procedure across the groups.

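### Five to twelve outcomes are tested with no primary outcome, error control or exploratory status, so a lone p<0.05 would be weak evidence

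*Combined protocol and SAP*

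**What the plan says.** The Objective is to "evaluate the use of real-time ultrasound (US) as a feedback device for transverse abdominis (TrA) activation/contraction during an exercise program". It points towards TrA activation without calling it primary.

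The Methods give one list of outcomes: "Outcome measures, test at baseline and post-intervention, include Numeric Pain Rating Scale (NPRS), TrA activation level", then "seven established motor control tests, Roland-Morris Disability Questionnaire (RMDQ) and Hospital Anxiety and Depression Scale (HADS"). Nothing in the list is marked primary or secondary. The text does not say whether the motor control tests are combined or analysed one by one, or whether HADS gives one score or two. On treatment, the Methods state: "The same motor control-based exercise program is applied to both groups".

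The Statistical Analysis Plan describes three layers of testing:

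- a mixed ANOVA, with group and time as factors, "to determine whether there were between- and within-group differences before and after treatment";
- independent and paired t-tests, which "are also used for differences between and within groups, respectively";
- a chi-square "test was also conducted for differences on the motor control tests and the TrA activation level procedure across the groups".

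It does not say which outcomes go into the ANOVA or what the t-tests add to it. It states no significance level, multiplicity adjustment, testing order or exploratory status. The title and the Objective call the study a pilot.

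**The concern.** When several outcomes are tested and none is singled out in advance, the chance that at least one reaches p<0.05 by luck is well above 5%. A reader then has no way to know whether a significant result concerned the question the trial set out to answer or was the one that happened to come up. The word pilot does not settle this. The stated analysis is hypothesis testing, and the plan does not say how a significant result is to be read.

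The planned within-group tests add a second difficulty. Both arms receive the same exercise programme, so patients in either arm may improve for reasons unrelated to ultrasound. A significant before-after change in the ultrasound arm would not show that the feedback helped; only a between-group contrast bears on that.

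It is also unclear whether the analysis of TrA, the outcome closest to the objective, makes use of the baseline measurement.

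**Working it through.** The plan gives no sample size, significance level or error rate, so it has no figure of its own to reproduce.

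**Step 1. Count the outcomes (Methods).** NPRS 1, TrA 1, motor control 1 or 7, RMDQ 1, HADS 1 or 2.

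- Motor control as one score: 1+1+1+1+1 = 5, or 6 with two HADS scores.
- Motor control tests taken separately: 1+1+7+1+1 = 11, or 12 with two HADS scores.

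**Step 2. Assumptions (none is in the document).** Two-sided 5% level; one between-group test per outcome (there are two arms, hence one contrast); no true effect on any outcome; equal correlation ρ between outcomes, from 0.3 to 0.7.

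**Step 3. Chance of at least one false positive among k tests.** With c = 1.96 and U standard normal:

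P = 1 − E_U{[Φ((c − √ρ·U)/√(1−ρ)) − Φ((−c − √ρ·U)/√(1−ρ))]^k}

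For a false positive favouring ultrasound, the second Φ term is left out. With independent outcomes the two formulas become 1 − 0.95^k and 1 − 0.975^k.

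Either direction / favouring ultrasound:

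| k | ρ = 0.3 | ρ = 0.5 | ρ = 0.7 | independent |
|---|---|---|---|---|
| 5 | 20.9% / 10.5% | 18.3% / 9.1% | 14.8% / 7.4% | 22.6% / 11.9% |
| 6 | 24.1% / 12.2% | 20.7% / 10.4% | 16.4% / 8.2% | 26.5% / 14.1% |
| 11 | 37.5% / 19.1% | 30.4% / 15.2% | 22.3% / 11.1% | 43.1% / 24.3% |
| 12 | 39.7% / 20.2% | 31.9% / 16.0% | 23.2% / 11.6% | 46.0% / 26.2% |

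Over ρ from 0.3 to 0.7 the range is 14.8% to 39.7%, or about 15–40% (7–20% favouring ultrasound).

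**Step 4. How far the range moves with other assumptions.**

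- *Small samples.* Simulated t-tests with an assumed 10, 15 or 30 patients per arm gave 14.9–21.5% for k = 5 and 23.2–40.5% for k = 12. The normal approximation is not driving the result.
- *Chi-square tests.* With k = 12, eight of the tests (TrA and seven motor control) would be chi-square. Simulating eight binary chi-square tests plus four t-tests (assumed 10–30 per arm, latent correlation 0.3–0.7, event rates 0.3–0.8) gave about 25–45% without continuity correction and about 16–32% with it. The plan does not say which would be used.
- *Duplicate tests.* Suppose the t-test on post-treatment values and the ANOVA group-by-time test are both read for NPRS, RMDQ and HADS, with a before-after correlation of 0.3–0.7. Simulation then gives 22–36% for 5–6 outcomes and 29–49% for 11–12. This is only one reading of an unclear text.

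**Step 5. What naming a primary does.** One primary test at 5% carries a 5% error on that claim (2.5% favouring ultrasound). If the other outcomes are still tested, the probabilities in the table do not change; those results simply no longer support a confirmatory claim.

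**The case against.** The strongest reply is that this is a pilot. The title and Objective say so, no efficacy claim is announced, and few readers would treat one nominal p-value from such a study as confirmation. That stands, and it limits the consequence. It does not supply what is missing: no outcome is ranked, and no sentence labels the tests exploratory.

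It can also be said that every input to the percentage is assumed. That stands too. The figure depends on the correlations, on how many tests each outcome receives, on the form of chi-square and on arm size, which is not stated. It illustrates the problem and is not a bound.

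Some stronger readings are tempting, but the documents do not support them:

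- *That the TrA analysis discards baseline.* A reader might infer this from the chi-square sentence. But that test is introduced as an addition, the ANOVA includes time and is never restricted to particular outcomes, and the chi-square could compare categories of improvement. The text leaves the matter open. Nor can a precision gain from baseline adjustment be quoted: the usual formula needs a continuous score, and a chi-square test suggests categories.
- *That within-group change will be offered as evidence for ultrasound.* The plan does not say so, and the ANOVA's group-by-time term addresses the right contrast. The point is only that the paired tests come with no limit on their interpretation.
- *That no significant result could be distinguished from chance.* This goes too far. A very small p-value would survive a Bonferroni threshold even over 12 outcomes (0.05/12 = 0.0042).

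**Conclusion.** The point holds as a gap in specification that should be closed. The plan tests 5 to 12 unranked outcomes with overlapping methods and no primary outcome, error control or exploratory status. Under the Step 2 assumptions the chance of some nominal false positive is about 15–40%. It would be higher with weaker correlation (up to 46% if outcomes are independent) or with duplicate tests, and lower with continuity-corrected chi-square tests in small arms. A lone p<0.05 would therefore be weak evidence, and a within-group change would be no evidence for the feedback itself.

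The absence of ranking and labelling can be read directly from the text; confidence in the exact percentage is much lower. A reader might infer that naming a primary brings 15–40% down to 5%. It does not: the two figures answer different questions. The first concerns any outcome, the second the single confirmatory claim.

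**What to change.** If the outcome data are unexamined, amend the Statistical Analysis Plan in one of two ways:

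1. Name the between-group comparison of post-intervention TrA activation, adjusted for its baseline, as the single primary analysis, and label all other outcomes exploratory. Use ANCOVA if the measure is continuous, or logistic or ordinal regression if it is categorical and numbers allow.
2. Label all outcomes exploratory and draw no efficacy conclusion from any single test.

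Under either, state what the t-tests add to the ANOVA, say whether the TrA analysis uses baseline, and base no conclusion on within-group tests.

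The text is partly in the past tense, so analysis may have begun. If data have been examined, label all outcomes exploratory or disclose the choice of primary as post hoc.

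The cost is wording only. Baseline is already collected, so no patients, visits or measurements are added. The downsides are that under the first option secondary results lose confirmatory standing, under the second no result has it, and categorical regression may be unstable if the arms are small.

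### NPRS, RMDQ and HADS: no planned between-group test adjusts for the baseline score; ANCOVA would usually be more precise at small cost

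*Combined protocol and SAP*

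**What the plan says.** Under Methods, patients are "randomly assigned to an US-guided or control group", and the outcome list reads "Outcome measures, test at baseline and post-intervention, include Numeric Pain Rating Scale (NPRS", continuing to "Roland-Morris Disability Questionnaire (RMDQ) and Hospital Anxiety and Depression Scale (HADS". There are two measurement times.

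The Statistical Analysis Plan applies a "two-way mixed analysis of variance (ANOVA) model for dependent measures of two factors (treatment group and time point of measurement", the second factor being the repeated one. It is "performed to determine whether there were between- and within-group differences before and after treatment". Independent-samples and paired t-tests "are also used for differences between and within groups, respectively".

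The plan does not say which ANOVA term is the treatment comparison, or whether the independent t-test uses post scores or changes. It names no baseline covariate. A separate chi-square "test was also conducted for differences on the motor control tests and the TrA activation level procedure across the groups"; those outcomes are outside this point.

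**The concern.** The baseline score of each measure is collected anyway, and in a randomised trial it is usually a useful predictor of the post score. Every between-group test listed for NPRS, RMDQ and HADS either fixes the weight given to that baseline in advance or, in the case of the ANOVA group main effect, targets a diluted quantity.

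Two things are at stake. One is precision: a fixed slope that is far from the true one leaves avoidable variance in the treatment estimate. The other is the error that remains once a particular chance baseline difference has occurred. In a pilot that difference can be sizeable, and a post-score test and a change-score test then err by different amounts, often in opposite directions. The plan does not say which to believe.

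**Working it through.** **Inputs.** From the document: two randomised groups, two measurement times, and the tests listed above. It states no sample size, SD, correlation, alpha or power, so there is no planned figure to reproduce. Assumed: n = 10 or 20 per arm, equal arms, bivariate normal scores, no dropout. Let rho be the pre-post correlation, k the post/baseline SD ratio, and baseline SD = 1.

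**Step 1: what each test estimates.**
- *Group-by-time interaction.* With two times this contrast is the difference in mean change. On two separate simulated data sets, the interaction F equalled the squared change-score t (1.4399 in one, 2.5504 in the other). The slope is fixed at 1.
- *Independent t-test.* The slope is 0 on post scores and 1 on change scores.
- *Group main effect.* It averages the two times, so its expectation is (0 + delta)/2. In simulation it averaged 0.40 for a true effect of 0.80.

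**Step 2: variance of each estimate, in units of 2/n.**
- Change score: 1 + k² − 2·rho·k
- Post score: k²
- ANCOVA: k²(1 − rho²)(1 + 1/(2n − 4))

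Example, n = 10, rho = 0.5, k = 1: change score 1 + 1 − 1 = 1; post score 1; ANCOVA 0.75 × (1 + 1/16) = 0.797. The ratio is 1/0.797 = 1.25, and its square root gives a standard error 12% larger. At n = 20, ANCOVA is 0.75 × (1 + 1/36) = 0.771, the ratio is 1.30 and the standard error is 14% larger.

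Variance relative to ANCOVA (10 per arm / 20 per arm):

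| rho | change, k=0.7 | change, k=1 | change, k=1.3 | change, k=1.5 | post score, any k |
|---|---|---|---|---|---|
| 0.3 | 2.26 / 2.33 | 1.45 / 1.50 | 1.17 / 1.21 | 1.08 / 1.12 | 1.03 / 1.07 |
| 0.5 | 2.02 / 2.09 | 1.25 / 1.30 | 1.03 / 1.07 | 0.98 / 1.01 | 1.25 / 1.30 |
| 0.7 | 1.92 / 1.99 | 1.11 / 1.14 | 0.95 / 0.98 | 0.94 / 0.98 | 1.85 / 1.91 |

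**Step 3: where ANCOVA loses.**
- The post score is more precise only if rho < 1/√(2n − 3): below 0.24 at 10 per arm, 0.16 at 20.
- The change score is more precise only if |1/k − rho| < √((1 − rho²)/(2n − 4)). At rho = 0.5 that means k from 1.40 to 3.53 (10 per arm) or 1.55 to 2.81 (20). At rho = 0.7 it means 1.14 to 1.92 or 1.22 to 1.72.
- For any rho and k, the largest loss is 1/(2n − 4): 1/16 = 6.25% at 10 per arm, 1/36 = 2.8% at 20.

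**Step 4: error given a chance imbalance.** The baseline difference has SD √(2/n): 0.45 at 10 per arm, 0.32 at 20. Per baseline SD of difference, the error in post-SD units is rho for the post score, −(1 − rho·k)/k for the change score and zero for ANCOVA. With a 0.30 SD difference and rho = 0.5, the post score is off by +0.15 at every k. The change score is off by −0.28, −0.15, −0.08 and −0.05 at k = 0.7, 1, 1.3 and 1.5. At k = 1 the two tests therefore differ by 0.30 SD through imbalance alone.

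**Step 5: simulation.** With 200,000 trials per setting and the slope fitted in each, variance ratios agreed with the formulas to within 0.02 and conditional errors to within 0.01; ANCOVA's conditional error was below 0.01. Type I error at rho = 0.5 was 4.9–5.1% for all three tests. On an assumed integer 0–10 scale (10 per arm, rho about 0.5) with 9%, 25% and 41% of post scores at the floor, variance relative to ANCOVA was 1.07, 1.18 and 1.42 for the change score and 1.31, 1.28 and 1.24 for the post score, again with type I error 4.9–5.1%. Dropout and unequal slopes were not simulated.

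**The case against.** The strongest reply is that nothing here is invalid. Over randomisation the interaction and the t-tests are unbiased and keep their type I error, and a pilot with no stated power target has no threshold that lower precision would make it miss. That stands: this is a matter of efficiency and conditional error, not a flaw that invalidates the trial.

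Second, every magnitude is assumed. The change score ranges from 2.33 times ANCOVA's variance to 0.94 times it, so how much this trial would gain cannot be shown. That also stands. The algebra of Step 1 needs no assumed sample size, SDs or correlation, however, and the loss bound depends only on n.

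Third, the price is more than a degree of freedom. Estimating the slope adds the factor 1 + 1/(2n − 4), which grows in very small samples: the worst loss is 1/12 = 8.3% at 8 per arm, 1/8 = 12.5% at 6 and 1/6 = 16.7% at 5. At 6 per arm, rho = 0.5 and k = 1.3, the change score is already slightly better: 1.39/(1.69 × 0.75 × 1.125) = 0.97. The claim of small cost therefore depends on the arms not being tiny.

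Fourth, the stated "objective was to evaluate the use of real-time ultrasound (US) as a feedback device for transverse abdominis (TrA) activation/contraction" concerns TrA, which has its own chi-square test. This point mainly serves the other measures. That limits its reach but does not answer it.

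**Conclusion.** The concern holds. For NPRS, RMDQ and HADS no planned between-group test estimates the baseline slope, although the baseline is collected and groups are randomised. The planned interaction and t-tests remain valid. ANCOVA would usually be more precise and would remove, to a close approximation, the error due to chance baseline imbalance.

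At 10 to 20 per arm the trade is lopsided: a variance loss of at most 6.25% or 2.8%, against unadjusted variances commonly 1.03 to 2.3 times ANCOVA's over the assumed range. The exceptions are a weak correlation (for the post score) or a post SD well above the baseline SD (for the change score). The sizes rest on assumed n, rho and k, equal arms, normal scores and no dropout, with one bounded-scale check in support. It is an improvement that should be made, not a condition of the trial's validity.

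**What to change.** For each of NPRS, RMDQ and HADS, name one between-group estimate: the ANCOVA of the post-intervention score on treatment group and the same measure's baseline score, reported as the adjusted mean difference with its 95% CI. Keep the mixed ANOVA and paired t-tests only to describe change over time, and state that neither the interaction nor the group main effect is the treatment estimate. Give the independent t-test a stated role, as an unadjusted supporting comparison, or drop it for these measures.

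If TrA activation is recorded as a number, analyse it the same way; if it is a category, leave it with its categorical plan. Which outcome is primary is a separate question that this change does not settle.

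The cost is SAP wording, one residual degree of freedom and the variance factor 1 + 1/(2n − 4), with no new data. The plan mixes present and past tense, so it does not show whether the analysis had already been done. If it had, report the ANCOVA and label it as added afterwards.

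### With no analysis population or missing-data rule, the mixed ANOVA and t-tests default to patients with a post-intervention value, and the two unadjusted contrasts can be pushed in opposite directions

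*Combined protocol and SAP*

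**What the plan says.** The whole plan is a short combined protocol and SAP. Under Methods, patients are "randomly assigned to an US-guided or control group", and "All patients receive physiotherapy twice per week for 7 weeks", which makes 14 sessions. Measurement is limited to two occasions: "Outcome measures, test at baseline and post-intervention".

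Under Statistical Analysis Plan, the main method is a "two-way mixed analysis of variance (ANOVA) model for dependent measures of two factors (treatment group and time point of measurement", with time as the only repeated factor. The SAP adds: "Independent samples' t-test and paired samples' t-test are also used for differences between and within groups, respectively". A chi-square test covers the motor control tests and TrA activation.

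The text does not say who is analysed, does not mention intention-to-treat, gives no expected dropout, and has no rule for a missing second measurement. It does not say whether patients who stop attending are still tested. It does not name one between-group contrast as the main one.

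**The concern.** The second measurement comes at the end of a 14-session programme, so patients who stop attending are the ones most likely to lack it. A standard two-time-point mixed ANOVA and a paired t-test drop a patient without the second value, and a post-score t-test cannot use that patient either. The comparison is then between those who stayed, which need not equal the effect of offering ultrasound feedback to those randomised.

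A second problem adds to this. The group-by-time interaction compares changes, and the between-group t-test, read as a post-treatment test, compares post scores. Neither adjusts for baseline. A baseline difference among the patients analysed, from selective dropout or from chance, shifts the two contrasts in opposite directions. In a small pilot they could disagree with no treatment effect present, and the plan does not say which to believe.

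**Working it through.** **Inputs.** From the document: two randomised arms, two time points, 2 × 7 = 14 sessions, and the named methods. It gives no sample size, dropout rate, SD, correlation or significance level, so there is no planned figure to reproduce and everything numerical below is assumed. Scores are in SD units with higher worse; the true effect is 0; the baseline-post correlation ρ is 0.3, 0.5 or 0.7; tests are two-sided at 5%. Differences are ultrasound minus control unless stated.

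**Step 1: do unequal dropout rates matter in themselves?** Large-sample simulation, ρ = 0.5, first arm minus second (originally in points with SD 2, divided by 2 here). Where dropout is related to a score, its log-odds change by 1 per SD.

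| Dropout | Post score | Change | Baseline-adjusted |
|---|---|---|---|
| 10% v 30%, unrelated to scores | 0.00 | 0.00 | 0.00 |
| 20% v 20%, same relation to post score | 0.00 | 0.00 | 0.00 |
| 10% v 30%, same relation to baseline | +0.08 | -0.08 | 0.00 |
| 20% v 20%, opposite relation to baseline | -0.17 | +0.18 | 0.00 |

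A difference in rates is neither sufficient (row 1) nor necessary (row 4). What matters is whether dropout shifts the completers' scores by different amounts in the two arms.

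**Step 2: dropout driven by baseline.** Ultrasound arm: 20% lost at random. Control: odds of loss rise e^1 = 2.7-fold per SD of worse baseline, about 24% lost. The completers' baseline means then differ by d = 0.204 SD. Because the expected post score is ρ × baseline:

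- post-score bias = ρd
- change bias = ρd − d = −(1 − ρ)d
- baseline-adjusted bias = ρd − ρd = 0

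| ρ | Post: ρd | Change: −(1 − ρ)d | Adjusted |
|---|---|---|---|
| 0.3 | +0.06 | -0.14 | 0.00 |
| 0.5 | +0.10 | -0.10 | 0.00 |
| 0.7 | +0.14 | -0.06 | 0.00 |

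Simulation agrees. If the arms lose opposite kinds of patient, d is about 0.41, and at ρ = 0.5 the biases are about +0.20 and -0.20.

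**Step 3: dropout driven by the post score.** Same strength, control only. The completers' post means differ by e = 0.204 and their baseline means by ρe. With β the within-arm slope among completers (0.28, 0.48, 0.68):

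- post-score bias = e
- change bias = (1 − ρ)e
- baseline-adjusted bias = (1 − βρ)e

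| ρ | Post | Change | Adjusted |
|---|---|---|---|
| 0.3 | 0.20 | 0.14 | 0.19 |
| 0.5 | 0.20 | 0.10 | 0.16 |
| 0.7 | 0.20 | 0.06 | 0.11 |

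Here adjustment does not remove the bias, and the change contrast is the least biased of the three.

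**Step 4: size against noise.** With an assumed 20 per arm, about 16 and 15.2 remain. The standard error of the post-score difference is √(1/16 + 1/15.2) = 0.36 SD, against biases of 0.06 to 0.14 in Step 2. Type I error there is about 0.05 to 0.07 for the two planned contrasts. With opposite baseline-driven loss it is about 0.08 to 0.09, against 0.05 adjusted. With opposite post-score-driven loss (ρ = 0.5) it is about 0.08 to 0.09 for change and 0.16 to 0.17 adjusted.

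**Step 5: precision with complete data.** Variance of the between-group difference, in units of σ²/n per arm: post score 2; change 4(1 − ρ); adjusted 2(1 − ρ²). At ρ = 0.5 these are 2.0, 2.0 and 2 × 0.75 = 1.5.

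**The case against.** The strongest reply is that the plan is silent rather than wrong. A reader might infer that it prescribes a completers' analysis. It does not: that follows from how the named methods normally run, and nothing excludes imputation or another rule. This stands, and the point is worded as a default.

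A reader might also infer that any difference in dropout between arms biases the result. Step 1 shows otherwise.

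It is tempting to treat baseline adjustment as the cure. Step 3 rules that out: if patients stop because of how they are doing, the adjusted estimate can be further from the truth than the interaction contrast. Its advantage for bias is confined to dropout explained by observed data.

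The magnitudes are modest. Chance alone gives the completers' baseline difference an SD of about 0.36, larger than the assumed dropout shift of 0.20, so a disagreement between the two contrasts would often be chance imbalance. That stands too, but it also supports adjustment, which deals with chance imbalance and gains precision even with no dropout.

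Finally, the SAP does not say which values the independent t-test compares. On change scores it would duplicate the interaction test and there would be no conflict; the ambiguity itself needs settling.

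**Conclusion.** The concern holds in a limited form. The plan leaves the analysed patients and the handling of missing post-intervention values undefined. Its methods then default to patients with a second measurement, and it offers two unadjusted contrasts that can conflict. Bias follows only if dropout is related to prognosis or outcome differently by arm, in the sense that the resulting shifts do not cancel.

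Under the assumed control-only scenarios the bias is 0.06 to 0.20 SD for the planned contrasts, with type I error close to nominal when dropout is baseline-driven. Only the extreme case of arms losing opposite kinds of patient takes the baseline-driven error rate to 0.08 to 0.09. These figures show direction and conditions; they do not predict this trial. The document does not support saying that its results are biased, or by how much.

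The change is worth making because it is cheap. Measuring patients who stop attending is the only step here that protects against outcome-driven dropout. One adjusted estimate removes the conflict, and at correlation 0.5 with complete data its variance is 1.5/2.0 = 75% of either planned contrast.

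**What to change.** 1. **Methods.** State that the post-intervention test at 7 weeks is attempted in every randomised patient whatever number of sessions was attended, for all outcomes including the motor control tests and TrA activation. This is the main protection.
2. **Statistical Analysis Plan.** For NPRS, RMDQ and HADS, replace the ANOVA interaction and the between-group t-test with one baseline-adjusted estimate per outcome: ANCOVA, or a linear mixed model with a common baseline mean. Analyse patients in their assigned group and report the 7-week group difference with a 95% CI.
3. **State the limit.** Say that the adjusted estimate removes dropout bias only when dropout is explained by observed data, and that if dropout depends on the post score it can be more biased than the change contrast. Report missing post-tests by arm for every outcome, including those tested by chi-square.

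The cost is a few sentences and some effort to bring back patients who stopped attending. No new visit or extra patients are needed, and the baseline values are already collected. If follow-up has already finished, item 1 becomes a report of who was tested; items 2 and 3 still apply.

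### For NPRS, RMDQ and HADS, no planned between-arm test adjusts for baseline as a covariate and none is named as the test of ultrasound; baseline-adjusted ANCOVA should be the deciding analysis for each scale

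*Combined protocol and SAP*

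**What the plan says.** The Objective is "to evaluate the use of real-time ultrasound (US) as a feedback device". Under Methods, patients are "recruited and randomly assigned to an US-guided or control group", and "The same motor control-based exercise program is applied to both groups". There are two measurement times: "Outcome measures, test at baseline and post-intervention".

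The Statistical Analysis Plan is one paragraph. Its main model is a "two-way mixed analysis of variance (ANOVA) model for dependent measures of two factors (treatment group and time point of measurement"), used "to determine whether there were between- and within-group differences before and after treatment". It then adds: "Independent samples' t-test and paired samples' t-test are also used for differences between and within groups, respectively". A chi-square test is kept for "differences on the motor control tests and the TrA activation level procedure across the groups".

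By elimination, the ANOVA and the t-tests apply to NPRS, RMDQ and HADS. The paragraph does not say which ANOVA term or which t-test answers the question about ultrasound. It does not say whether the independent t-test compares post-treatment values or changes, and it mentions no baseline covariate. This point concerns the three scales only, not the outcomes sent to the chi-square test.

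**The concern.** Both arms receive the same exercises, so only a between-arm contrast can show what ultrasound adds. The plan allows three such contrasts, and they are not interchangeable:

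- **Group-by-time interaction.** With two time points this equals a t-test on change from baseline.
- **Independent t-test on post-treatment values.** This ignores baseline.
- **Group main effect of the ANOVA.** This averages baseline and post-treatment. Randomisation makes the expected baseline difference zero, so it estimates only half of a post-treatment effect.

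In small arms, a chance baseline difference pushes the post-only comparison one way and the change comparison the other. The two can therefore disagree, and the plan has no rule for that case. ANCOVA estimates the baseline slope from the data, removes the shift on average and gives a narrower interval.

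The paired tests describe response to the exercise programme and cannot isolate ultrasound. The plan does not claim that they do.

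**Working it through.** **Inputs.** From the document: two randomised arms, and baseline and post-treatment scores on each scale. Not in the document, so assumed: 10 to 20 patients per arm (n), 1:1 allocation, equal SDs, normal scores, two-sided 0.05, and baseline-post correlation r of 0.3 to 0.7. The plan states no sample size or power, so there is no figure of its own to reproduce.

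**Large-sample variance of the treatment estimate, relative to a post-only t-test**

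| Analysis | Formula | r = 0.3 | r = 0.5 | r = 0.7 |
|---|---|---|---|---|
| Post-only t-test | 1 | 1.00 | 1.00 | 1.00 |
| Interaction (change) | 2(1 - r) | 1.40 | 1.00 | 0.60 |
| Group main effect, rescaled to the full effect | 2(1 + r) | 2.60 | 3.00 | 3.40 |
| ANCOVA | 1 - r² | 0.91 | 0.75 | 0.51 |

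**Cost of estimating the slope.** The ANCOVA variance is multiplied by 1 + 1/(2n - 4). At n = 15 this is 1 + 1/26 = 1.038, which gives 0.95, 0.78 and 0.53.

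**Break-even points.**
- ANCOVA beats post-only when r exceeds √(1/(2n - 3)): 0.24, 0.19 and 0.16 for n = 10, 15 and 20.
- ANCOVA beats the interaction when r is below 2(2n - 4)/(2n - 3) - 1: 0.88, 0.93 and 0.95.

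**Chance imbalance.** At 15 per arm the baseline difference has SE √(2/15) = 0.37 SD and exceeds one SE in about 32% of trials. A one-SE difference shifts post-only by r × 0.37 and the interaction by (r - 1) × 0.37. These are +0.18 and -0.18 SD at r = 0.5, and +0.26 and -0.11 SD at r = 0.7.

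**Simulation.** 40,000 trials per setting; n = 10, 15, 20; r = 0.3, 0.5, 0.7; true effect 0, 0.5 or 0.8 SD. With no effect, each test rejected in 4.8% to 5.2% of trials. Results at 15 per arm (power is for 0.8 SD):

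| | r = 0.3 | r = 0.5 | r = 0.7 |
|---|---|---|---|
| Power, ANCOVA | 58.6% | 66.7% | 83.2% |
| Power, interaction | 43.1% | 56.0% | 78.3% |
| Power, post-only | 56.4% | 55.9% | 56.1% |
| Power, group main effect | 25.9% | 22.8% | 21.3% |
| Mean 95% CI half-width (SD), ANCOVA | 0.72 | 0.65 | 0.54 |
| Half-width, interaction | 0.88 | 0.74 | 0.57 |
| Half-width, post-only | 0.74 | 0.74 | 0.74 |

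ANCOVA had the highest power in all 18 settings with a true effect.

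**Disagreement, if the independent t-test is on post-treatment values.** At 15 per arm, r = 0.5 and 0.8 SD, at least one of post-only and interaction rejects in 72.9% of trials. Exactly one rejects in 2 × 72.9 - 55.9 - 56.0 = 33.9%. Over all settings the range is 29% to 41% at 0.8 SD and 18% to 40% at 0.5 SD. With no effect, at least one of the two rejects in 8.8% to 9.6%.

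**The case against.** **The planned tests are valid, and the ANOVA already uses baseline through the interaction.** Both statements are true. The criticism is only that baseline is not a covariate: change scores fix its slope at 1, a post-only test fixes it at 0, and ANCOVA estimates it. This is a matter of efficiency and clarity, not of a wrong error rate.

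**The independent t-test may be meant for change.** It would then be identical to the interaction, and the disagreement and 9% figures would vanish. That stands, so those figures are conditional; the 9% also matters only if either test may carry the conclusion. The precision loss and the unnamed contrast remain on either reading.

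**The gain is uneven.** Against the better of post-only and interaction at 15 per arm and 0.8 SD, ANCOVA adds about 2, 11 and 5 percentage points of power at r = 0.3, 0.5 and 0.7. The comparison with the group main effect is the harshest one, and nothing says conclusions rest on that term. However, r is unknown in advance, so the planners cannot tell which unadjusted test will be the better one.

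**Naming the interaction would end the ambiguity without ANCOVA.** It would, but at 15 per arm it is less precise than ANCOVA for any r below about 0.93.

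**The fix leaves other matters open.** This also stands. Three scales each tested at 5% give 1 - 0.95³ = 14.3% if independent, no primary outcome is named, and TrA activation, the outcome closest to the objective, is not reached. These are separate issues.

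**Conclusion.** The concern holds. For the three scales, no planned between-arm test adjusts for baseline as a covariate, and the plan does not say which contrast decides the effect of ultrasound. Those two facts come from the text and need no assumption.

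The size of the benefit does rest on assumptions. For r of 0.3 to 0.7, ANCOVA's large-sample variance is 0.91 to 0.51 of the post-only test's and 0.65 to 0.85 of the interaction's. ANCOVA would be slightly less precise than post-only only if r fell below about 0.16 to 0.24, and less precise than the interaction only if r exceeded about 0.88 to 0.95.

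The plan should be changed, but this is not an error that invalidates any planned test. In a pilot, the main return is a narrower interval and one unambiguous result per scale.

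**What to change.** State in the Statistical Analysis Plan, for each of NPRS, RMDQ and HADS:

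- Conclusions about ultrasound rest on the between-group difference in the post-treatment score adjusted for the baseline score (ANCOVA), reported with a 95% CI.
- The group-by-time interaction is a supporting analysis; if it disagrees, the ANCOVA result stands.
- The ANOVA group main effect and the unadjusted independent t-test are not used for conclusions.
- Within-group mean changes are reported with 95% CIs and labelled descriptive.

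The cost is a few sentences, one model per scale and one degree of freedom. No new patients or measurements are needed. The plan mixes present and past tense, so it is not clear whether results had been seen when it was written. If they had, the change should be dated and reported as made after the data were seen.
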